3. STUDY SUMMARY

Title:	Observational Study of Outcomes after EchoMark and EchoSure-based Free Flap Monitoring
Protocol Number:	2019-1
Design:	This is a prospective, single arm, non-randomized, multi-center observational study to demonstrate the performance of the EchoMark and EchoSure devices in patients undergoing free flap surgery.
Study Duration:	Projected enrollment of first patient: March 2019 Projected exit of final patient: November 2019
Primary Objective:	The primary objective of the study is collect data on patient outcomes in cases where the surgeon has chosen it as the appropriate method of monitoring.
Patient Population:	Patients undergoing free flap surgery.
Sample Size:	Up to four hundred (400) patients will be enrolled.
Number of Sites:	Up to eight (8) sites.
Treatments:	One or two EchoMark soft tissue marking devices will be placed and monitored using the EchoSure system for 72 hours.
Endpoints:	
Primary Performance Endpoints:
 
 Surgeon evaluation of improved monitoring ability and satisfaction 
Secondary Performance Endpoints:
 
 Flap failure rate Flap takeback rate Flap salvage rate Total cost of hospitalization Time from OR departure to return to OR Nurse evaluation of improved monitoring
NCT Number	03915717

Inclusion Criteria	
 • Age \geq 18 years • Patients presenting for microvascular tissue transfer procedures where the surgeon selects EchoMark and EchoSure as an appropriate method of monitoring. • Patient is able to sign informed consent and able to participate in all testing associated with this clinical investigation • Women of childbearing potential have a negative pregnancy test
Exclusion Criteria	
 • Age <18 years old • Patient unable to sign informed consent • Patient participating in another investigational device or pharmacological study • Prisoner or patient from vulnerable populations as defined in 45 CFR 46.
Follow Up:	Patients will have no follow-up responsibilities following their discharge from the index surgical procedure.

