5. STUDY OBJECTIVES

Purpose

The purpose of this study is to evaluate the performance of the EchoMark and EchoSure (both FDA approved devices) as an ultrasound-based method of monitoring the viability of free flaps and patency of at-risk vessels. The implant and ultrasound will be used per IFU. The primary purpose of the study is to collect data on patient outcomes in cases where the surgeon has chosen it as the appropriate method of monitoring.

Performance Goals

Primary Performance Endpoint:

- Surgeon evaluation of improved monitoring ability and satisfaction

Secondary Performance Endpoints:

- Flap failure rate
- Flap takeback rate
- Flap salvage rate
- Total cost of hospitalization
- Time from OR departure to return to OR
- Nurse evaluation of improved monitoring

Safety Goals

Primary Safety Endpoint:

- Procedure freedom from Serious Adverse Events (SAEs) during the EchoMark implantation procedure, hospitalization, and at discharge.

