7. STUDY POPULATION

Number of Patients

Up to four hundred (400) patients will be enrolled and both men and women will be eligible for inclusion. The estimated enrollment period is nine months and patients will be followed until discharge from their index surgical procedure.

Intended Use

The EchoMark and EchoSure devices are intended to be used by a trained medical professional. The EchoMark device is intended to be a Single Use Device, used in a surgical operating suite or equivalent setting. The EchoSure device is reusable and may be used in the operating suite or a post-operative unit such as the ICU or patient floor. When used intraoperatively or in the presence of breached skin, the EchoSure Probe should be used with a sterile probe cover.

Inclusion Criteria

- Age \geq 18 years

- Patients presenting for microvascular tissue transfer procedures where the surgeon has selected EchoMark and EchoSure as the optimal method of vascular monitoring based on clinical assessment and plan
- Patient is able to sign informed consent and able to participate in all testing associated with this clinical investigation
- Women of childbearing potential have a negative pregnancy test

Exclusion Criteria

- Age <18 years old
- Patient unable to sign informed consent
- Patient participating in another investigational device or pharmacological study
- Prisoner or patient from vulnerable populations as defined in 45 CFR 46.

PATIENT WITHDRAWAL FROM THE STUDY

Patients are free to withdraw consent at any time. Patients who wish to terminate their participation in the research will no longer receive ultrasound examinations of their free flap and their data will be removed from the study.

8: STATISTICAL ANALYSIS

Statistical power was calculated based on determination of the number of detected thrombosis events needed to see a difference between EchoSure and an alternate method of flap monitoring (e.g., clinical examination). A one-tailed paired t-test was used to compare the dichotomous outcome of whether EchoSure detected a thrombotic event prior to other methods of monitoring. At $\alpha=0.05$ and $\beta=0.80$ with a medium Cohen's effect size of 0.5, 27 thrombotic events are needed for comparison. With a baseline national re-exploration rate of about 7%, an enrollment of 385 patients will provide sufficient sample size for the analysis.

9: PATIENT ENROLLMENT AND CONSENT

Method of Subject Identification and Recruitment

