10. STUDY PROCEDURES AND METHODS

Patients undergoing free flap procedures will be identified. No additional clinic visits or additional hospital stay will be required of any study participant. All monitoring of skin or soft tissue will be carried out in the same manner. EchoMark will be implanted prior to closing the patient following the Instructions for Use on the FDA-approved labelling.

The flap will be non-invasively monitored with the EchoSure ultrasound intraoperatively and postoperatively. Intermittent ultrasound monitoring will be performed postoperatively at the institutional standard flap check protocol (q1 hours in first 24 hours, q2 hours in hours 24-48, and q4 hours thereafter) until the patient is discharged from the hospital. Presence of arterial and venous flow will be recorded. Images and/or video clips will be saved.

Actions to Be Taken by Site Staff	Screening and pre-operative evaluation	Surgery Date	Each Scan	Discharge
Consenting	X			
Initial Enrollment Form		X		
Nurse Scan Form		X	X	
EchoSure Scan			X	
Standard Clinical Exam			X	
End of Trial Period Form				X

11: DATA COLLECTION, ANALYSIS, AND MONITORING

Participating surgeons and nurses will complete a brief survey (see CRFs in appendix) capturing their assessment of whether they felt EchoMark and EchoSure improved their ability to monitor free flaps. Surgeons will complete a short form detailing the clinical characteristics and outcome of the case (e.g., whether there was a vascular flow problem and how it was detected). This, and the data management and storage, will be managed by the PI.

Source Documentation

The Investigator must maintain complete source documents on all trial patients who are enrolled in the trial or who undergo screening. Source documents include patient medical records, hospital charts, clinic charts, Investigator's patient trial files, as well as the results of diagnostic tests (e.g., laboratory tests) kept in an individual patient binder and stored in a secured and locked location and must be made available to the sponsor or designated monitor during site visits.

The following minimum information should be recorded in the patient's medical records:

- The date the patient entered the trial and the patient number
- The trial protocol number and the name of the Sponsor
- The date that informed consent was obtained
- Evidence that the patient meets trial eligibility requirements (e.g., medical history, trial procedures and/or evaluations)

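### The only sample-size calculation is for an EchoSure-detects-first comparison that no endpoint list contains, so its power applies neither to the primary surgeon survey nor to any other listed endpoint

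*Combined protocol and SAP*

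**What the plan says.** Section 8 holds the plan's only sample-size statement. It rests on "the number of detected thrombosis events needed to see a difference between EchoSure and an alternate method of flap monitoring". The outcome is dichotomous, "whether EchoSure detected a thrombotic event prior to other methods of monitoring", and is compared with a one-tailed paired t-test at alpha 0.05 and a Cohen's effect size of 0.5. It concludes that "27 thrombotic events are needed for comparison" and, using a national re-exploration rate of about 7%, that "an enrollment of 385 patients will provide sufficient sample size for the analysis".

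The endpoints are in Section 3 (Endpoints) and Section 5 (Performance Goals, Safety Goals). The primary performance endpoint is "Surgeon evaluation of improved monitoring ability and satisfaction". The six secondary ones are the flap failure, takeback and salvage rates, hospitalization cost, time from leaving the OR to returning to it, and the nurse evaluation. Section 5 adds a primary safety endpoint, freedom from serious adverse events.

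On data collection, Section 11 says: "Participating surgeons and nurses will complete a brief survey (see CRFs in appendix". It does not say whether a surgeon answers once or once per case. A separate surgeon form covers, as an example item, "whether there was a vascular flow problem and how it was detected". The schedule table in Section 10 puts the EchoSure scan and the standard clinical exam in the same column, with no stated order between them.

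**The concern.** A sample-size statement tells the reader what the study can conclude, and here it answers a question that the endpoint lists do not ask. Two things follow. A report that keeps to Sections 3 and 5 could omit the one comparison for which the study was sized. And a reader who sees a power calculation beside a named primary endpoint may link the two, although the calculation says nothing about the survey.

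There is a related weakness in how the powered outcome would be recorded. If both methods find a problem at the same check and the order is not fixed, which one counts as first may depend on which was done or written down first. That could favour EchoSure without any real advantage.

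**Working it through.** **1. Reproduce the stated size.** Inputs from Section 8: d = 0.5, one-sided alpha 0.05, and 0.80 (printed as beta, but it works only as power). For a paired t-test on n events, power = P(T > t(0.95, n−1)), where T is noncentral t with noncentrality d√n.
- n = 26: noncentrality 0.5 × √26 = 2.550, critical value 1.708, power 0.798.
- n = 27: noncentrality 0.5 × √27 = 2.598, critical value 1.706, power 0.812.

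So 27 is the smallest n that reaches 0.80, as stated. Enrolment: 27 / 0.07 = 385.7, against 385 stated. There is no doubt about which comparison set the size.

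**2. Match the powered outcome to the endpoints.** Section 3 lists 1 primary and 6 secondary performance endpoints, and Section 5 adds 1 safety endpoint: 8 in all. None is detection order. The nearest, time to return to the OR, does not record which method found the problem. The count is 0 of 8.

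**3. What the 81% is conditional on.** Expected events = 385 × 0.07 = 26.95. With X binomial(385, 0.07), P(X ≥ 27) = 0.524. At the cap of 400 patients it is 0.606. This takes every re-exploration as a thrombotic event. The documents give no thrombosis rate, and if only some re-explorations are for thrombosis the expected count falls in proportion.

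**4. Why the recording order matters (illustration).** Score each event +1 if EchoSure was first and −1 otherwise. The t-test on 27 events then rejects from 18 upward: 18 of 27 gives t = 1.80 > 1.706, and 17 gives 1.37. Suppose EchoSure has no true advantage, and a share s of events is found by both methods at the same check (10%, 20% or 30%, assumed).

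| s | Same-check events counted as not EchoSure-first: P(X ≥ 18), success probability (1−s)/2 | Same-check events all credited to EchoSure: P(X ≥ 18), success probability (1+s)/2 |
|---|---|---|
| 0% | 0.061 | 0.061 |
| 10% | 0.019 | 0.153 |
| 20% | 0.005 | 0.309 |
| 30% | 0.001 | 0.516 |

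The first scoring is the one that Section 8's wording implies, and it does not inflate false positives. The last column is a worst case that a fixed order rules out.

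**5. Survey precision (illustration).** The text shown does not give the unit of response. The surgeon numbers and intraclass correlations below are assumptions; Section 3 gives only "Up to eight (8) sites".
- One response per surgeon, with 1, 2 or 3 surgeons at each of 8 sites: 6/8, 13/16 and 19/24 favourable give Wilson 95% intervals of 41–93%, 57–93% and 60–91%.
- One independent response per case: 308/385 (80%) gives 76–84%, a half-width of 1.96 × √(0.16/385) = 4.0 points.
- One response per case, clustered within J surgeons: design effect = 1 + (385/J − 1) × ICC. J = 24 and ICC 0.1 give 2.50, a half-width of 4.0 × √2.50 = 6.3 points. J = 8 and ICC 0.5 give 24.56, a half-width of 19.8 points.

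**The case against.** The strongest reply is that this is a single-arm observational study meant to collect outcome data, and a descriptive survey endpoint needs no power. That stands: the point is not that the survey must be powered. But the plan chose to justify its size with a hypothesis test, so it should say which endpoint the test serves.

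It can also be said that Section 8 already names the outcome, direction, test and alpha, that Section 4 gives a rationale (little comparative data), and that the surgeon form supplies a data source. All true. A reader might infer that the comparison is unspecified or has no test, and the documents do not support that. What it lacks is a place among the endpoints. Because Section 8 names its outcome, a careful reader is also less likely to attach its power to the survey.

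The case report forms are not shown. They may settle the survey unit and the recording order, and the form schedule in Section 10, arranged by patient stage, leans towards per-case completion without proving it. They cannot put the comparison into endpoint lists that are shown in full.

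Two stronger readings should be resisted. One is that same-check detections leave d = 0.5 undefined and erode the 81%. Section 8's outcome is yes or no over all 27 events, and a same-check detection is not prior detection, so it already counts as no; the effect size applies to that outcome, and the power is 81% if 27 events occur. The other is that the survey is shown to be imprecise. The wide intervals above come from assumed surgeon numbers and correlations, not from the plan.

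**Conclusion.** The concern holds as a mismatch between the size justification and the endpoints, not as an arithmetic error. The sole power statement (27 events, 385 patients, 0.812) belongs to a comparison that is none of the eight listed endpoints, and the primary performance endpoint has no stated power or precision. These two facts rest on the text alone.

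The 52% chance of reaching 27 events assumes a true 7% rate and that every re-exploration is a thrombotic event. The recording-order and survey figures are illustrations under the assumptions given with them, and the verdict does not depend on them.

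This should be fixed, but it is not a bar to the study. A reader might infer that 385 patients are of no use for the listed endpoints. That does not follow: 27 takebacks in 385 would give 7.0% with a Wilson 95% interval of 4.9 to 10.0%. That is simply not the justification that Section 8 offers.

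**What to change.** 1. **Sections 3 and 5:** list the proportion of confirmed thromboses first detected by EchoSure, versus another method, as a named endpoint. Secondary status is enough.
2. **Section 8:** state that the 27-event calculation and its power apply only to that endpoint and are conditional on 27 events. Give the chance of reaching that number (about 52% with 385 patients at a true 7% rate) and say that 7% is a re-exploration rate. Report the surgeon survey descriptively: the proportion, a 95% confidence interval, the number of surgeons responding, and whether the unit is the case or the surgeon. If it is the case, the interval should allow for repeat responses by the same surgeon.
3. **Sections 10 and 11,** unless the case report forms already do this (then cite them): at each shared check, record the clinical exam finding before the EchoSure result is seen, count detection by both at the same check as not EchoSure-first, and report how many such events there were. This concerns the order of recording only, not the check schedule or the response to a finding.

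**Cost:** items 1 and 2 are wording, and make the power statement less favourable than the present one. Item 3 is a real if modest burden. By the schedule in Section 10 there are 24 + 12 = 36 checks per patient in the first 48 hours, or 36 × 385 = 13,860 over the study, with further checks until discharge. The changes themselves add no enrolment, but neither do they make 385 patients certain to yield 27 events.

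### Section 8 rests its only power statement on a paired t-test and Cohen's d of 0.5 for a dichotomous outcome, with no assumed EchoSure-first proportion; an exact test of that outcome has about 70% power at d = 0.5, not 80%

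*Combined protocol and SAP*

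**What the plan says.** Section 8 (Statistical Analysis) contains the plan's only power calculation and the only test it names. The test is described so: "A one-tailed paired t-test was used to compare the dichotomous outcome of whether EchoSure detected a thrombotic event prior to other methods of monitoring". Alpha is 0.05, and 0.80 is given as the value of beta. The size then follows: "with a medium Cohen's effect size of 0.5, 27 thrombotic events are needed for comparison". A national re-exploration rate of about 7% converts events to patients: "an enrollment of 385 patients will provide sufficient sample size for the analysis". Section 7 sets the ceiling: "Up to four hundred (400) patients will be enrolled".

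Three other places bear on the point.

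- The schedule table in Section 10 marks both the EchoSure scan and the "Standard Clinical Exam" in its column for each scan.
- Section 11 has surgeons record "whether there was a vascular flow problem and how it was detected".
- Section 5 lists "Surgeon evaluation of improved monitoring ability and satisfaction" as the primary performance endpoint. Detection order is not among the primary or secondary endpoints there or in the study summary.

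No section gives an assumed proportion of events that EchoSure finds first, a null proportion, or an explicit rule for events that both methods find at the same check.

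**The concern.** A paired t-test and Cohen's d describe the mean of a continuous difference in units of its standard deviation. For an outcome that is yes or no for each event, power depends on the proportion of events found first by EchoSure and on the share that are tied. Neither is stated, so a reader cannot tell what advantage the study could detect or with what probability.

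Section 8 names the t-test for sizing and does not say which test will be used on the data. In a sample of about 27 events that choice can decide the result: with no ties, 18 of 27 is significant by the t-test and not by an exact test. The documents as shown leave this open. The case report forms, which might define detection order, are not shown.

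The patient number carries a further assumption, that the re-exploration rate equals the rate of thrombotic events.

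**Working it through.** **Inputs from Section 8:** one-sided alpha 0.05; d = 0.5; 27 events; rate 7%; 385 patients. Proportions, tie rates and any other event rate below are assumptions, because the documents give none.

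**1. The plan's own figure.** Noncentral-t power for a one-sided paired t-test at d = 0.5 is 0.798 for n = 26 and 0.812 for n = 27, so 27 is the smallest n that reaches 0.80. This works only if 0.80 is power rather than beta. Then 27 / 0.07 = 385.7 and 385 × 0.07 = 26.95. The stated figures reproduce.

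**2. What d = 0.5 means with no ties.** Score each event +1 (EchoSure first) or −1 (other method first). The mean is 2p − 1 and the variance is 4p(1 − p), so d = (2p − 1) / (2√(p(1 − p))). Setting d = 0.5 gives (2p − 1)² = 0.2 and p = 0.7236.

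**3. The t-test on 27 untied events.** At 18 of 27 the mean is 9/27 = 0.333, the SD is √(27/26 × (1 − 0.333²)) = 0.961, and t = 0.333 / (0.961/√27) = 1.80, against a critical value of 1.71. At 17 of 27, t = 1.37. The test therefore rejects at 18 or more. The true size is P(X ≥ 18 | 27, 0.5) = 0.061.

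**4. The exact sign test on untied events.** At 27 events it rejects at 19 or more, with size 0.026.

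| Untied events | Rejects at | Size | Power at 72.4% | Power at 75% |
|---|---|---|---|---|
| 26 | 18 | 0.038 | 0.725 | 0.820 |
| 27 | 19 | 0.026 | 0.681 | 0.786 |
| 28 | 19 | 0.044 | 0.776 | 0.862 |

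The event count cannot be fixed in advance. Averaged over Binomial(385, 0.07), power is 0.709 at 72.4% and 0.803 at 75%.

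**5. With ties scored 0.** With tie rate t and proportion q among untied events, the mean is (1 − t)(2q − 1) and the variance is (1 − t) − mean². Holding d at 0.5 gives (2q − 1)² = 0.2 / (1 − t). For t = 0.2, q = 0.75: mean 0.4, variance 0.64, d = 0.5. For 27 events in total:

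| Ties | q for d = 0.5 | t-test size | t-test power | Exact power |
|---|---|---|---|---|
| 0% | 72.4% | 0.061 | 0.812 | 0.681 |
| 5% | 72.9% | 0.047 | 0.771 | 0.703 |
| 10% | 73.6% | 0.046 | 0.767 | 0.711 |
| 20% | 75.0% | 0.049 | 0.779 | 0.719 |
| 50% | 81.6% | 0.050 | 0.800 | 0.711 |

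If q is held at 75% instead, exact power falls from 0.786 with no ties to 0.719 with 20% and 0.493 with 50%. For 385 patients at 7%, with 75% EchoSure-first and 20% ties, the figure averaged over the event count is 0.707.

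**6. The event rate.** If thrombotic events occurred in 5% of patients (an assumption), 385 × 0.05 = 19.25 events would be expected. Exact power without ties, averaged over the count, would be 0.56 at 72.4% and 0.66 at 75%.

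**The case against.** The strongest reply is that the t-test does reasonably well in the setting this design makes likely. The scan and the clinical exam share a check, so ties are plausible, and with 5–50% ties the t-test's size is 0.046–0.050 and its power 0.77–0.80, close to what Section 8 claims. This stands. A reader might infer that the planned test inflates the false-positive rate in general; the calculation shows that only with no or almost no ties (0.053 at 2%).

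Second, 68% is a low point of a discrete test: power is 72% at 26 events and 78% at 28. This also stands, and the averaged 71% is the fairer figure.

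Third, the outcome is worded as detection prior to other methods, so read literally a simultaneous detection counts as not first. That reading is available, but it would need a justified null. With 20% ties and no difference between methods, EchoSure would be first in 0.8 × 0.5 = 40% of events, so a 50% null would not represent equality.

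Fourth, detection order is not a listed endpoint and the t-test is named only for sizing. Both are true, and they limit the weight of the point. They do not supply the missing proportion.

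**Conclusion.** The concern holds in limited form. The only power statement in the plan uses a continuous-outcome method for a dichotomous outcome, states no EchoSure-first proportion or explicit tie rule, and mislabels power as beta. An exact test of that outcome at d = 0.5 has 68% power for 27 untied events, 71% averaged over the event count for 385 patients at 7%, and 70–72% with 5–50% ties among 27 events. These figures rest on scoring events +1, −1 or 0; those for 385 patients also need thrombotic events to occur at the 7% re-exploration rate.

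Two stronger readings are not supported. The sample-size arithmetic is not wrong: 27 and 385 follow from the stated inputs. Nor is the study's main analysis compromised, because the primary endpoint is the surgeon evaluation and no listed endpoint depends on detection order. The severity is minor to moderate.

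**What to change.** In Section 8, replace the paired t-test sentence with wording such as:

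> EchoSure-first will be compared with other-method-first by a one-sided exact sign (McNemar) test at alpha = 0.05. Events found by both methods at the same check are ties; they will be counted, reported and left out of the test. The EchoSure-first proportion among untied events will be given with its exact one-sided 95% lower bound. Power is about 71% for 385 patients, assuming 75% EchoSure-first among untied events, 20% ties, and a thrombotic event rate equal to the 7% re-exploration rate.

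The 75% and 20% are examples. The sponsor should put in its own assumptions, label them as such and recompute the power. Also change beta = 0.80 to power = 0.80, and have the sponsor state whether detection order is an endpoint or a supporting analysis.

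The cost is a change of wording and one line of analysis code, plus a check that the case report forms record which method found each event first and when both did so at the same check. No enrolment change is needed. The downsides are a less favourable stated power and, when ties occur, some loss of power against the t-test (0.72 against 0.78 at 20% ties and 27 events).

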6. STUDY DESIGN

This is a prospective, single arm, non-randomized, multi-center observational study to record subjective and objective data in patients undergoing free flap surgery where the surgeon has chosen to use the EchoMark and EchoSure devices for flap monitoring.

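### Section 8 asks which method detected a thrombosis first, but both are read at the same flap check with no stated recording order, independence or tie rule, so the comparison is open to bias

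*Combined protocol and SAP*

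**What the plan says.** Section 8 (Statistical Analysis) bases the sample size on "whether EchoSure detected a thrombotic event prior to other methods of monitoring". It analyses this yes/no outcome with a one-tailed paired t-test and concludes that "with a medium Cohen's effect size of 0.5, 27 thrombotic events are needed for comparison". It then converts events to patients: "With a baseline national re-exploration rate of about 7%, an enrollment of 385 patients will provide sufficient sample size for the analysis".

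Section 10 (Study Procedures and Methods) fixes the timing: "Intermittent ultrasound monitoring will be performed postoperatively at the institutional standard flap check protocol". That means hourly for 24 hours, two-hourly to 48 hours and four-hourly after that. The procedures table ticks Nurse Scan Form, EchoSure Scan and Standard Clinical Exam in the same *Each Scan* column. Arterial and venous flow is recorded, and images or clips are saved.

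Section 11 has the surgeon complete a short form on the characteristics and outcome of the case, including "whether there was a vascular flow problem and how it was detected". This is the only described statement of how a problem came to light.

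The device description in Section 4 says flow is displayed in real time and that a nurse or other provider can use the device at the bedside. The background in the same section calls inspection subjective and dependent on the examiner.

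**The concern.** *First* needs either two times or two independent readings at a common time. The plan provides a common time but does not say the readings are independent. Within one check, nothing in the supplied text says which assessment is done first, whether the same person does both, or whether one finding is written down before the other is known. Someone who has seen absent flow may examine the flap differently, and someone who has seen a discoloured flap may scan differently.

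If both methods are abnormal at the same check, the credit can follow the order of looking or a later judgement by the surgeon. Once either finding leads to action, the time at which the other method would have turned abnormal is no longer observed.

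At stake is a false claim of earlier detection. Early detection is part of the hypothesis in Section 4, and this comparison is the stated basis for the number of patients.

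**Working it through.** **1. The plan's own figures.** Inputs from Section 8: one-sided α = 0.05, effect size d = 0.5, and β = 0.80, which reproduces the result only if read as power 0.80.

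- Paired t-test power = P(T > t(0.95; n−1)), where T is noncentral t with n−1 degrees of freedom and noncentrality d√n.
- n = 26 gives 0.798 and n = 27 gives 0.812, so 27 events is reproduced.
- Patients: 27 / 0.07 = 385.7. The plan states 385, and 385 × 0.07 = 26.95 expected events.

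The arithmetic is sound. The problem lies in what is being counted.

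**2. What the schedule can resolve.** These are the patterns possible at a single check:

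| EchoSure | Clinical exam | Order visible? |
|---|---|---|
| Abnormal | Normal | Yes, EchoSure first |
| Normal | Abnormal | Yes, exam first |
| Abnormal | Abnormal | No, a tie at that check |

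The first two rows are trustworthy only if neither recorded reading was altered by knowledge of the other. The third row has no rule in the plan.

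**3. Size of the possible bias (illustration).** Take 27 events and no true lead.

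- A one-sided sign test at 0.05 needs at least 19 of 27, since P(X ≥ 18) = 0.061 and P(X ≥ 19) = 0.026 at probability 0.5.
- Let a share t of events be ties, credited to EchoSure with probability q. Untied events split 50:50.
- The chance that an event is counted as EchoSure first is π = tq + (1 − t) × 0.5. The false-positive chance is P(X ≥ 19 | 27, π).

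The documents give neither t nor q. With q = 0.7 assumed:

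| Tie share t | π | Chance of a significant result |
|---|---|---|
| 1.00 | 0.70 | 58% |
| 0.50 | 0.60 | 18% |
| 0.25 | 0.55 | 8% |

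If all events are ties, the chance is 2.6% at q = 0.5, 18% at q = 0.6, 58% at q = 0.7 and 79% at q = 0.75. The sign test is not the planned test, but this choice does not inflate the figures. On +1/−1 scores the planned one-tailed paired t-test already rejects at 18 of 27 (p = 0.042).

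**4. Power if ties are kept as ties.** Score each event +1 (EchoSure first), 0 (tie) or −1 (exam first).

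- With no ties, d = 0.5 means a mean score of 0.447 and SD 0.894, so EchoSure is first in (1 + 0.447)/2 = 72.4% of events. Hold that share among untied events.
- Then the mean is (1 − t) × 0.447, the SD is √[(1 − t) − mean²], and d is their ratio.

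| Tie share (assumed) | d | Power with 27 events | Events for 80% power | Patients at 7% |
|---|---|---|---|---|
| 0% | 0.50 | 0.81 | 27 | 386 |
| 25% | 0.42 | 0.69 | 37 | 529 |
| 50% | 0.33 | 0.52 | 58 | 829 |

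The loss is not inevitable. If every untied event favoured EchoSure, exact sign-test power would still be about 1.00 at 50% ties and 0.84 at 75%.

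**The case against.** A reader might infer that the design cannot show EchoSure detecting first at all. The documents do not support that. An abnormal scan beside a normal exam, with the exam abnormal only at a later check, is observable under the present schedule. A shared check time limits resolution but does not abolish order.

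Four further objections carry weight.

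- **The CRFs.** They are cited as an appendix that is not in the supplied text. The Nurse Scan Form may already hold exam findings, order or times. This stands as a caveat, but a time field alone would not stop one reading influencing the other, and Section 8 would still lack a definition of *first* and a tie rule.
- **Who does what.** Only the scan form is named as the nurse's. The text does not say who performs the clinical exam, so a single nurse doing both is a possibility and not a stated fact.
- **Which record is analysed.** Section 8 does not say it will use the surgeon's attribution, and flow records and images exist as well. The plan leaves the source open, so reliance on the surgeon's form cannot be assumed or excluded.
- **Importance.** Detection order is neither a primary nor a secondary endpoint in Section 5, and the stated primary purpose is to collect outcome data. That limits the weight of the point. It does not remove it, because the sample size rests on this comparison.

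The 58% figure is also the extreme case in which every event is a tie, and it should not be quoted alone.

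**Conclusion.** The concern holds in this form: as described, the plan can show order across checks but cannot give an unbiased comparison of which method detected first. The gap is in recording order, independence of readings, definition of detection time and handling of ties.

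With 27 events, no true lead and an assumed 70% of ties credited to EchoSure, the chance of a spurious significant result is 8% to 58% as the tie share rises from a quarter to all events. Without such a tilt it is 2.6%. The tie share and the 70% are assumptions.

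The plan's 27 events reproduce but make no allowance for ties, so the 80% power holds only if ties are few. The finding rests on the supplied text and should be checked against the CRFs. It should be put right, though it does not touch a listed endpoint.

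**What to change.** Subject to checking the CRF appendix:

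1. **Section 10 and the Nurse Scan Form.** Have the standard clinical exam finding entered and time-stamped before the EchoSure result at that check is viewed.
2. **Section 8.** For events later confirmed surgically, define three outcomes from the paired records: *EchoSure first* (EchoSure abnormal, recorded exam normal), *exam first* (the reverse) and *same check* (both abnormal). Report same-check events, and events noticed between checks, as separate categories. Do not rely on the surgeon's end-of-case attribution.
3. **Flow calls.** Base them on the recorded arterial and venous flow and the saved images. Acknowledge that the EchoSure reading is still made with knowledge of the exam, because exam-first recording removes only one direction of influence.
4. **Sample size.** State that the 27-event calculation makes no allowance for ties and that its 80% power holds only if ties are few. At an assumed 50% ties, the illustration above needs about 829 patients against the cap of 400.

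The cost is at most a field and a time stamp on an existing form, plus a few sentences. The downsides are a fixed recording order at every check, and a result and power that may be less favourable. Section 9 tells patients that participation does not alter their care, so the recording step should be worded consistently with that. No change to when clinicians act on a finding is implied.
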